2 OUTCOMES^{CT.GOV;ERSCH}

2.1 Primary Outcome

The primary goal of this trial is to test initial efficacy of health coaching relative to brief advice. The primary outcome that this trial is powered to detect is change in alcohol use (defined as average weekly drinking) from baseline to one month follow-up (pre-operative outcome) and from baseline to the four month follow-up (post-operative outcome) in the Health Coaching condition relative to the brief advice condition.

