All baseline and follow-up assessments will be designed and administered using the Qualtrics Research Suite (<http://www.qualtrics.com>). The project-specific Qualtrics site is protected with a researcher-designated login name and password. The site houses the surveys and compiles data that staff will then transfer to a password protected Access database on the Department of Psychiatry secure network. For the web-based follow-up surveys, participants receive an email invitation inviting them to take the survey on-line and directing them to the Qualtrics site. An additional password may be given to participants in order for them to access to the site. There are systems in place that prevent the survey from being taken by the same user more than once. No identifying information is linked to the participants. There are security precautions in place to protect against unauthorized access, but there is a small risk of unauthorized access. Information regarding Qualtrics security and privacy statements can be found at <http://www.qualtrics.com/security-statement> and <http://www.qualtrics.com/privacy-statement>.

Baseline and Follow-up assessment. Baseline and Follow-up assessments will be completed by participants online (via tablet or home computer) at baseline, at 1-month follow-up (approximately one-week pre-surgery), and at 4-months follow-up (approximately three months' post-surgery). The schedule of assessments is indicated in the Schedule of Study Activities. Participants will be notified by e-mail or text message when they are scheduled to complete follow-up. If participants do not have internet access or do not want to complete the baseline or follow-up assessment online, research staff will conduct the follow-up assessment over the telephone, reading the questions from Qualtrics.

Self-Report Measures

Alcohol use assessments administered at baseline and follow-up include the Alcohol Use Disorders Identification Test (AUDIT)¹¹, the Alcohol Timeline Followback (TLFB)¹², the Severity of Alcohol Dependence Questionnaire (SADQ-C)¹³. The primary outcome (average weekly drinking using the TLFB) is gathered here. All other self-report measures are exploratory.

Measures of alcohol use problems, behaviors, and cognitions include the Short Inventory of Problems (SIP)¹⁴, the Penn Alcohol Craving Scale (PACS)¹⁵, the Readiness-to-Change Ruler¹⁶, Situational Confidence Questionnaire (SCQ)¹⁷.

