8 STATISTICAL CONSIDERATIONS^{ERSCH}

8.1 Sample Size

Sample Size and Power Considerations. The sample size ($N = 90$) was primarily chosen to facilitate conclusions regarding study feasibility, acceptability, and provide experience with study protocol (e.g. recruitment, retention, assessment, and analysis). Participant retention ($n = 72$; 80%) is achievable using methods utilized in mentor's past research^{27,28} and described in the retention section. A final sample of 72 participants will provide power of .80 to detect a medium effect ($f^2 = .20$) using the proposed analyses. Based on meta-analyses of MI for excessive drinking, medium effects are expected within a 4-month follow up period^{29,30}. Between group differences in post-operative morbidity, mortality, and healthcare utilization will likely be 'very small' based on base-rates of postoperative complications. This study is underpowered to detect small effects. For this reason, hypothesis testing is considered 'exploratory.' Therefore, this study will primarily provide pragmatic information and experience with the study protocol to inform a fully-powered RCT.

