8.2 Data Analyses^{ct.gov}

8.2.1 General Approach

Data Preparation. Prior to analyses, we will examine patterns of missing data, research dropout, intervention fidelity, distributional properties of measures, correlations among outcome measures³¹. Given the small sample, we will pay particular attention to data distribution and use transformations when appropriate.

Data Analysis. We will examine between group effects on alcohol use using General Estimated Equations (GEE). We expect balanced groups on key variables as a result of urn randomization but will test the following covariates for systematic effects on outcome; gender, age, race/ethnicity, surgery type, and drug use. These analyses will use regression modeling using GEE due to the correlated structure of our data from repeated measures at baseline and follow-up. The GEE methodology properly estimates the regression coefficient and variance of the regression coefficient when correlated data are used in regression analysis will use all data available for participants including those subjects lost to attrition. Appropriate distributions will be used based on the nature and distribution of the response variable. Relevant covariates will be included such as gender, age, race/ethnicity, surgery type, smoking status, and drug use.

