8.2.2 Primary Outcome

The primary outcome of this study is between group differences in change in alcohol use from baseline to follow-up. This is defined as change in average weekly alcohol use (quantity by frequency) as measured by the Time Line Follow Back. Our hypothesis is: Relative to the brief advice group, the health coaching group will experience greater reductions in average weekly alcohol use between baseline and follow-up. This

hypothesis is considered exploratory given the low power to detect significant differences.

Qualitative Analysis:

All qualitative interviews will be digitally audio-recorded and transcribed verbatim using a HIPAA-compliant transcription service. Transcripts and codes will be analyzed using Nvivo software. We will analyze data using applied thematic analysis. Emerging themes and data interpretations will be used for intervention refinement.

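### The primary GEE treats baseline drinking as one of the repeated outcomes and does not name it as a covariate, giving up precision that the collected data could supply

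*Combined protocol and SAP*

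**What the plan says.** Section 8.2.1 of the combined protocol and SAP places baseline on the outcome side of the model: "These analyses will use regression modeling using GEE due to the correlated structure of our data from repeated measures at baseline and follow-up". Section 8.2.2 defines the effect: "The primary outcome of this study is between group differences in change in alcohol use from baseline to follow-up". Section 2.1 applies this to two intervals, baseline to 1 month and baseline to 4 months.

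The baseline value is available. Section 6 lists the TLFB among the measures taken at baseline and follow-up, and adds: "The primary outcome (average weekly drinking using the TLFB) is gathered here".

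Section 8.2.1 has two covariate sentences. The first says the analysts "will test the following covariates for systematic effects on outcome; gender, age, race/ethnicity, surgery type, and drug use". The second says relevant covariates go into the model and gives six examples: the same five plus smoking status. Baseline drinking is in neither. The second list is illustrative, so baseline is not excluded.

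No model equation, working correlation or constraint on the baseline means is given. The scale is also open: "Appropriate distributions will be used based on the nature and distribution of the response variable". Section 6.2.3 says the urn balances on gender only.

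**The concern.** With baseline in the outcome vector and no stated constraint, the usual model has arm, time and arm-by-time, with separate baseline means in each arm. Its arm-by-time term is a difference in mean change. That subtracts the whole baseline value, where regression would subtract only the part that predicts follow-up. Unless the two coincide, the result carries extra noise. Baseline drinking is likely to be strongly prognostic, and the urn does not balance it, so chance imbalance is left to the analysis.

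The stake is precision, not bias. Section 8.1 says "this study will primarily provide pragmatic information and experience with the study protocol to inform a fully-powered RCT". A narrower interval for the arm difference serves that purpose.

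The covariate wording raises a second issue. If covariates may be kept or dropped after testing them against outcome, the primary estimate depends on a choice made once outcome data are in view.

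**Working it through.** **Plan's own figure.** The plan states no precision for the arm contrast. Its nearest figure is in section 8.1: 72 of 90 retained (0.80 × 90 = 72) and power .80 for f² = .20. With noncentrality 0.20 × 72 = 14.4 and level 0.05 (assumed), a joint F test of five predictors has power .815, one of six has .781, and a 1-df arm contrast has .963. The stated .80 is therefore matched only as a joint test of five or six predictors. Nothing below depends on it.

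**Inputs.** From the documents: 45 per arm and 80% retention, so 36 completers and 9 lost per arm if losses are equal. Assumed: correlation ρ between any two visits of .3, .5 or .7; baseline SD 1; SD k at both follow-ups, with k = 1, 0.75 or 1.25; identity link; lost participants contribute baseline only.

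**Complete data.** The per-person variance is 1 + k² − 2ρk for change and k²(1 − ρ²) after adjustment. The difference is (1 − ρk)², which is never negative and is zero only when ρk = 1. At k = 1 the ratio of adjusted to change variance is (1 + ρ)/2 = .65, .75, .85. A simulation (36 per arm, three visits, 1,000 replicates) gave .644, .738, .859. In it the free-baseline GEE coefficient equalled the raw difference in mean change to rounding error. At these ratios, matching 72 adjusted participants would take a change contrast on 72/.65 = 111, 72/.75 = 96 or 72/.85 = 85.

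**With 20% loss.** For a free-baseline GEE with exchangeable working correlation α, put a = ρk − α and b = 1 − α:

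- Free baseline: 2 × {k²(1 − ρ²)/36 + a²/36 + (b² − 2ab)/45}
- Baseline as covariate: 2k²(1 − ρ²)/36

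Here α is the pooled value [ρ(2k + k²)/3] ÷ [(45 + 72k²)/117], which equals ρ when k = 1.

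Example, ρ = .5 and k = 1: a = 0 and b = .5. Free baseline is 2 × (.75/36 + .25/45) = .0528. Adjusted is 2 × .75/36 = .0417. The saving is 1 − .0417/.0528 = 21%.

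| k | ρ | Free baseline | Adjusted | Saving |
|---|---|---|---|---|
| 1 | .3 | .0723 | .0506 | 30% |
| 1 | .5 | .0528 | .0417 | 21% |
| 1 | .7 | .0323 | .0283 | 12% |
| 0.75 | .3 | .0552 | .0284 | 48% |
| 0.75 | .5 | .0409 | .0234 | 43% |
| 0.75 | .7 | .0262 | .0159 | 39% |
| 1.25 | .3 | .0964 | .0790 | 18% |
| 1.25 | .5 | .0715 | .0651 | 9% |
| 1.25 | .7 | .0453 | .0443 | 2% |

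If the free-baseline GEE used an independence working correlation (α = 0), its variance at k = 1 would be 2 × {1/36 + (1 − 2ρ)/45} = .0733, .0556, .0378, and the savings 31%, 25% and 25%.

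**Finite-sample cost.** Estimating the baseline slope from 72 completers adds about 1/(72 − 4) = 1.5% to the adjusted variance. The smallest cell becomes .0443 × 1.015 = .0449 against .0453, a gain of under 1%.

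**Common baseline mean instead.** Keeping baseline as an outcome, but with one mean for both arms and visit-specific SDs, gives the covariate model's variance in all nine cells. The working covariance matters. At ρ = .7 and k = 1.25, exchangeable gives .0459, unstructured correlation with one scale .0471 and independence .0868. All are worse than the change contrast at .0453; visit-specific SDs give .0443.

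**The case against.** The strongest reply is that the defect is inferred. A GEE with a common baseline mean fits section 8.2.1 as well, and with equal SDs and exchangeable correlation it already has the full gain. The covariate list is also open. This is fair. What can be said is that the text does not fix the estimator and that its ordinary reading is the less precise one.

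Second, the consequence is limited. Section 8.2.2 itself says the "hypothesis is considered exploratory given the low power to detect significant differences", section 8.1 chose the sample size mainly for feasibility and acceptability, and a change contrast is legitimate. This bears on the weight of the point. It is no reason to leave precision unused.

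Third, the size is driven by assumptions. This stands: ρ and the SD ratio are not in the documents, and the identity-link figures do not carry over directly to a log link or a transformed outcome.

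Fourth, randomisation alone gives unbiasedness only with complete data. With 20% loss, an unweighted GEE also needs dropout to be completely at random, or random given the modelled covariates. This also stands, and it applies to the adjusted model too.

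Fifth, the caution about an exchangeable working structure in the common-baseline alternative rests on a reversal of about 1% in one cell; in the other eight it beats the change contrast. That is correct. However, a single scale is never better than visit-specific SDs in these cells and is worse whenever the SDs differ.

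**Conclusion.** The concern holds as a matter of efficiency and specification; it is not an error of validity. On the ordinary reading, the primary estimate is a free-baseline change contrast. Adjusting for baseline TLFB would remove 12% to 30% of its variance at equal SDs and correlations of .3 to .7. Across the SD ratios examined the range is 2% to 48%, with the lowest cell close to zero after the slope cost. The larger savings arise if follow-up drinking is less variable than baseline. That is plausible because both interventions aim at abstinence, but the documents do not establish it.

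These figures rest on assumed correlations and SDs, an identity link, equal 20% loss with no intermittent missingness, and large-sample variances. The direction is firmer than the size: with complete data, baseline adjustment cannot lose in large samples to the change contrast.

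The covariate wording needs repair in its own right, because it gives two lists and allows a reading in which tests against outcome decide the model.

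**What to change.** In sections 8.2.1 and 8.2.2, write out the primary model: a GEE on the 1-month and 4-month TLFB values, with baseline TLFB (on the outcome or link scale) and gender as fixed covariates, plus arm, time and arm-by-time. Report the arm difference at each follow-up. State that participants with no follow-up value do not enter this model, and reconcile that with the statement in 8.2.1 that all available data are used, including from those lost to attrition. State the dropout assumption.

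Alternatively, keep baseline in the outcome vector with a common mean across arms and an unstructured working covariance whose SD may differ by visit. In that form, do not use independence, and do not rely on a structure with one common scale.

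Replace the two covariate sentences with one list, fixed before outcome data are seen and not selected by tests against outcome. Which further covariates it holds is the sponsor's choice.

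The cost is SAP wording only, since every variable is already collected. Leaving out participants without follow-up costs no precision against the common-mean model with visit-specific SDs when 20% are lost in each arm.

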5.4 Intervention Discontinuation

Withdrawal of consent will result in true study discontinuation with no interview or assessment performed. Any information collected before withdrawal will be kept as part of the subject's record. The study will document the patient's reason for withdrawal, if available, to track for study purposes.

Patients can also be withdrawn by the study if they become ineligible after consent. These reasons include (1) surgery cancelation or rescheduling with a greater than 6-month delay, (2) demonstrating substantial cognitive impairment at two time points as evidenced by lack of orientation to person, place, or time or lack of ability to repeat back and answer questions; or (3) displays or shows evidence of psychotic symptoms, (4) fails to follow instructions of the researchers.

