6.2.3 Randomization and Retention

Computer-generated urn randomization²⁶ will ensure balanced groups based on gender. Research staff will be blind to participant study condition (with the exception of those delivering interventions). We will track participant retention as a measure of study feasibility. Retention strategies include, collecting multiple forms of participant and collateral contact information and sending reminders by e-mail, phone, and text. We aim to retain 80% of patients (72/90) using these strategies and those used in mentors' past research that achieved similar rates of retention.

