6.2.5 Outcome Assessments

The change alcohol use and acceptability assessments will occur at three times throughout the study: baseline, one-month post-baseline, and four-months post-baseline. See List of Study Activities Table. We will verify alcohol and drug use reports through a blood draw and urine drug screen conducted on the day of surgery that will undergo lab testing for drug/alcohol biomarkers.

Qualitative Interviews

A total of 20 patients, 10 from each intervention condition, will be selected (based on response vs. non-response to intervention. Response is defined as an alcohol use reduction of greater than one standard deviation from the mean between baseline and final follow-up. Non-response is defined as any increase in alcohol use between baseline and final follow-up or no change in alcohol use. These participants will be asked to complete exit interviews regarding their experience. Qualitative interviews with patients occur during a single interaction with research staff. Qualitative interviews will be audio recorded. We will initially focus our patient interviews on what factors led to change or lack of change in alcohol use, and how the intervention played a role in these changes, and how the intervention could be improved.

6.2.6 *Withdrawal*

If subjects withdraw or decline to finish treatment, we will make every effort to gather primary outcome data at regularly scheduled follow-ups. We will also query for an adverse event over the phone or in person. For subjects who wish to withdraw completely from the study, we will make every effort to collect the data as soon as possible – i.e. when the individual lets you know of their decision to withdraw. We will continue to use data that was obtained prior to withdrawal date unless the participant asks for it to be destroyed. The data will be kept secure until it is destroyed.

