The Principal Investigator (PI) ultimately will be responsible for monitoring the data safety and quality with involvement from study coordinator. Data will be collected using the Qualtrics survey platform and or/standardized paper forms and will only be identified with the study ID of the participant. The codes that link the name of the participant and the study ID will be kept separately and securely, along with any signed consent forms obtained. Quality control and reliability of screening, baseline and follow-up assessments will be monitored by [name] throughout the trial via regular meetings and observation of the research staff conducting standardized assessments. Additional data will be stored in a study database created within the REDCap application. The quality of the data will be monitored throughout the study. Data will be analyzed using a data analysis program such as SAS software. Data quality will be monitored by random inspection of the completed forms by the research staff and any problems detected will be discussed with the PI.

Qualitative interviews will be conducted by trained research staff. The qualitative interviews will be audio-recorded. The audio-recordings of the sessions and interviews will be uploaded to a secure network server with restricted access. Once collected, participant data will remain confidential.

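### Must the GEE analysis name its working correlation, variance correction and missing-data assumption before its 4-month contrast can be trusted?

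*Combined protocol and SAP*

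**What the plan says.** Section 8.2.1 is the whole modelling plan for the primary outcome. It selects GEE because baseline and follow-up values from one person are correlated, and describes the method so: "The GEE methodology properly estimates the regression coefficient and variance of the regression coefficient when correlated data are used in regression analysis". The same sentence runs on to say that the analysis "will use all data available for participants including those subjects lost to attrition". On data preparation it promises to look first at missing-data patterns, dropout, distributions and correlations among outcome measures, and adds: "Given the small sample, we will pay particular attention to data distribution and use transformations when appropriate".

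No section names a working correlation, a variance estimator, a missing-data assumption or a missing-data sensitivity analysis. On software, the data monitoring plan in section 7.6 says only: "Data will be analyzed using a data analysis program such as SAS software".

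Other sections set the context. Section 2.1 makes change to one month and change to four months the two primary readings. Sections 6.2.3 and 8.1 plan to keep 72 of 90 participants. Sections 8.1 and 8.2.2 call the hypothesis testing exploratory.

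**The concern.** The description of GEE holds in large samples and concerns correlation. It does not address loss to follow-up, yet the sentence moves straight on to participants who were lost, as if the method took care of them.

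Two things could go wrong with about 36 completers per arm. First, with independence as the working correlation, the 4-month mean in each arm comes from completers alone. If heavier drinkers drop out more in one arm than in the other, the contrast shifts even when the interventions do not differ. Second, the usual robust variance is somewhat too small in small samples, so a z-test rejects a little too often.

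At stake is the 4-month estimate of initial efficacy, which would also inform a later, fully powered trial. No confirmatory claim depends on it.

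**Working it through.** **Inputs from the document.** 90 randomised, 45 per arm (section 1.2). Retention 80%: 90 x 0.80 = 72, or 36 per arm, so the plan's own figure reproduces. Three assessments (section 6.2.2).

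**Inputs that are assumptions.** The document gives no SD, correlation, alpha or loss mechanism. Assumed: two-sided 5%; log-normal drinking with log-SD 0.8 and a median of 15 drinks/week at baseline and 10 at follow-up; analysis of log(1+drinks) with a saturated arm-by-time model; no true effect; 20% loss at 4 months. Where loss is informative, its log-odds rise by 1 per SD of 1-month drinking, in one arm only. Three sets of correlations between visits were used: .3/.2/.35, .6/.45/.65 and .75/.65/.8.

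**Step 1: bias under independence, by hand.** Let p be the probability of loss and Z the standardised 1-month value. With mean p = 0.20 and slope 1, numerical integration gives E[p(1-p)] = 0.1386. Completers in the affected arm then have mean Z = -0.1386/0.80 = -0.173. The SD of log(1+drinks) at median 10 is 0.711. The shift in the 4-month contrast is (1-month to 4-month correlation) x (-0.173) x 0.711:

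| Correlation | Shift | Ratio, exp(shift) |
|---|---|---|
| .35 | -0.043 | 0.96 |
| .65 | -0.080 | 0.92 |
| .80 | -0.098 | 0.91 |

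Simulation of 20,000 null trials at the middle correlations gave -0.083, a ratio of 0.92. That is 0.083/0.177 = 0.47 of the standard error. Across all correlation sets, with 0 or 30% zeros at follow-up, the ratio was 0.86 to 0.96.

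**Step 2: the same loss with exchangeable correlation.** Those lost at 4 months now contribute through their earlier values. At the middle correlations the shift is -0.009, a ratio of 0.99; across all settings the ratio is 0.96 to 0.99. Under random loss the SD of the contrast is .171 against .177 for independence, so precision is not lost.

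**Step 3: the same loss mechanism in both arms.** The two shifts cancel. The ratio is 1.00 with either structure.

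**Step 4: a harsher check.** Normal outcome, correlation 0.5, and loss related to drinking in opposite directions in the two arms. Bias is -0.187 SD under independence (95% interval coverage 88.1%) and -0.009 SD under exchangeable (94.3%).

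**Step 5: loss driven by unseen 4-month drinking in one arm.** Without zeros the shift goes from -.128 (independence) to -.077 (exchangeable), a reduction of 1 - .077/.128 = 40%. With 30% zeros it goes from -.200 to -.147, a reduction of 1 - .147/.200 = 27%. Naming a correlation would not settle this case.

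**Step 6: variance correction (Mancl-DeRouen with a t reference).** Random loss, middle correlations: the uncorrected z-test rejects 5.3% (independence) and 5.4% (exchangeable); the corrected test rejects 4.4% with either. Monte Carlo error is about 0.15 points. An excess of 0.3 to 0.4 points becomes a shortfall of 0.6, and intervals widen by 4.4 to 4.7%. With informative loss in one arm and exchangeable correlation, rejection goes from 6.1% to 5.0%.

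**The case for a change.** The strongest case for a change runs as follows. Differential loss is easy to imagine: Health Coaching asks for two sessions of about 50 minutes and Brief Advice for one of about 10, and section 5.4 lets the study withdraw people who do not follow instructions. Nothing in the plan rules out independence, and the correlations it will examine may be those between instruments rather than between visits. Initial efficacy is the stated primary goal, so the estimate matters even if the p-value does not. If skewed drinking were modelled on a log link without transformation, the uncorrected z-test would reject 6.8 to 8.3%. Fixing the structure takes one line and prevents a choice made after seeing results.

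Much of this is true as a conditional statement. The wording of section 8.2.1 claims more than GEE delivers under informative loss, and naming a structure would do no harm. But the harm needs two events together, neither of which the plan states. An analyst who picks GEE because repeated measures are correlated, and who reviews dropout first, has every reason to use a non-independence structure. The log-link figure sets aside the plan's stated attention to skewness and transformation.

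The design also limits loss tied to arm. Follow-up surveys are the same in both arms, and for participants who cannot or will not respond online, "research staff will conduct the follow-up assessment over the telephone, reading the questions from Qualtrics". Section 6.2.6 seeks primary outcome data at the scheduled follow-ups from people who stop treatment, and section 6.2.3 lists retention measures.

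One textual conflict does exist. Section 5.4 says "Withdrawal of consent will result in true study discontinuation with no interview or assessment performed", while section 6.2.6 says "For subjects who wish to withdraw completely from the study, we will make every effort to collect the data as soon as possible". These passages should be reconciled, but they concern data collection and do not bear on the choice of correlation or variance.

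Nor is there a simple add-on for heavier drinking among the missing. The shortcut (share missing) x ln(factor) gives .2 x ln 2 = .139, but on log(1+drinks) a doubling shifts the contrast by about .127 without zeros and .089 with 30% zeros.

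**Conclusion.** No change is needed. The missing working correlation and missing-data assumption are a gap in detail, not a rule that gives a wrong answer. If the analysts used independence and loss followed 1-month drinking in one arm only, a null 4-month contrast would read about 0.92 at the middle assumed correlations (0.86 to 0.96 over the range tried). With the structure that the plan's own reasoning points to, it would read 0.96 to 0.99. With a shared loss mechanism there is no bias under the null.

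The variance correction is a separate matter, affecting test size and coverage but not bias. After transformation and under random loss it exchanges slight excess for slight conservatism, which is no clear gain in an exploratory pilot.

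These sizes rest on assumed distributions, correlations and loss slopes, because the document gives none. The conclusion would weaken if the analysts did adopt independence and retention turned out to depend on drinking differently by arm. The planned look at missing-data patterns gives the analysts a chance to see that before modelling.
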